4.4.1 Randomization procedure

At screening, participants will be assigned an identification number on a first-come, first-served basis. When it is confirmed that the participant is eligible for the clinical trial, he/she will be randomized.

The assignment of each participant to a particular treatment arm (experimental and control group will be performed in a 1:1:1:1 ratio) will be done by using an electronic system, which is centrally administered.

Near Infrared Transcranial Laser Therapy in Subjects with Major Depressive Disorder: A study of Dosing with Laser.

For each participant at each visit, the investigator or center coordinator will communicate with the central statistician and, through a user and password assigned for the center, will enter the web system where he/she will be able to request and obtain the corresponding treatment number assigned to him/her in the study, and then proceed with the laser application. The participants and the study investigator will be blinded to the treatment assignment. The screen of the medical device does not show information of the dose applied to each participant, only the group to which he/she belongs will be referenced, keeping the dosing details confidential.

At central level, the unblinded statistician (responsible for administering this web system) will know which treatment arm corresponds to each participant from each research center.

4.4.2 *Blinding procedure*

This study is a clinical trial where blinding of both the investigator and the study participant will be assured. Only the treatment identifiers, the central statistician of the study, will know the treatment identifiers.

The sponsor is responsible for providing the medical device under study, programming and maintenance of the device.

The investigator at each center will be responsible for providing the corresponding dose according to the intervention under study (treatment assigned by the statistician through the web system) to each study participant.

Simulation blinding will be effective because the radiation is not visible and because no dose from the NIR-TLT will produce any perceptible difference from the simulation patient, e.g., skin heating.

4.4.3 *Contingency plan for opening of the blind*

Only in the event of an emergency or serious adverse event or other particular event that alters the risk-benefit profile of the intervention will the principal investigator determine whether unblinding of a participant's study intervention assignment is warranted. Participant safety should always be the first consideration in making such a determination.

If the investigator decides that unblinding is warranted, every effort should be made to communicate this decision by telephone or mail to the sponsor or medical monitor before unblinding a participant's treatment assignment, unless this would delay the management of unblinding of the participant, as approval from either is necessary to communicate with the unblinded statistician responsible for the administration of the randomization web system, who has access to the arm assignment lists for each participant, to forward this information to the requesting site.

The date and reason for breaking the blind should be recorded in the source documents and in the FRCe by the investigator at the research site.

Near Infrared Transcranial Laser Therapy in Subjects with Major Depressive Disorder: A study of Dosing with Laser.

If the treatment assignment blind is opened, this information should only be shared with the other investigating doctors at the center on a need-to-know basis (especially when the cause is a safety event consistent with a serious adverse reaction). Treatment assignment information should not be shared with others, unless decided by the investigator or mandated by the regulatory authority.

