3.2 Overview of LiteCure Laser System

The EXPi device is a research device based on LiteCure's EXPi Deep Tissue Laser Therapy™ system. For this research study, the EXPi system's beam delivery, Empower™, is modified to deliver NIR laser energy non-invasively to the brains of subjects diagnosed with neuropsychiatric disorders. Other than the cap, the EXPi device is the same device as LiteCure's EXPi system: model LTS-2500, which is marketed under FDA 510(K) # K173067. The device is manufactured and supplied by LiteCure LLC, [name].

The EXPi device is a Class II medical device according to 21 CFR 890.5500 and 878.4810 and is manufactured according to 21 CFR 820. It uses laser diode sources that emit in the near infrared (808 +/- 10 nm) with a maximum continuous output of ≤ 30 watts. The device consists of two main assemblies: a console and an optical delivery system. Laser power is generated and controlled within the console assembly and delivered to the optical delivery system: custom helmet (cap), via a flexible double-clad optical fiber. The cap is configured to produce a 4 cm diameter (12 cm²) beam of light at each of two sites on the subject's forehead: adjustable at/near EEG locations F3 and F4.

The console is programmed to produce laser energy in one of 4 modes:

1. Mode 1 (BCW group), NIR-TLT dose:
 - i. Treatment site(s): EEG F3 and F4
 - ii. Time format:
continuous wave
 - iii. Average radiance: 350 mW / cm²
 - iv. Exposure time: 429 sec.
 - v. Total fluidity delivered: 3.6 kJ (1.8 kJ per treatment location)
2. Mode 2 (BPW-1 group), NIR-TLT dose:
 - i. Treatment site(s): EEG F3 and F4
 - ii. Time format: wave
pulsed, 10 Hz; 50% duty cycle
 - iii. Average radiance: 350 mW / cm²
 - iv. Exposure time: 429 sec.
 - v. Total fluidity delivered: 3.6 kJ (1.8 kJ per treatment location)
3. Mode 3 (BPW-2 group), NIR-TLT dose:
 - i. Treatment site(s): EEG F3 and F4
 - ii. Time format: pulsed wave, 40-50 Hz; 50% duty cycle
 - iii. Average radiance: 350 mW / cm²

Near Infrared Transcranial Laser Therapy in Subjects with Major Depressive Disorder: A study of Dosing with Laser.

- iv. Exposure time: 429 sec.
- v. Total fluidity delivered: 3.6 kJ (1.8 kJ per treatment location)

4. Mode 4 (SHAM group), NIR-TLT dose:

- i. Treatment site(s): none
- ii. Time format: none
- iii. Average radiance: 0 mW / cm²
- iv. Exposure time: 429 sec.
- v. Total fluidity delivered: 0 kJ

See section 4.3 - Dosing rationale

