4.17.2 Safety Monitoring

Study subjects will undergo frequent clinical assessments including depressive scores, concomitant medications, adverse events, and serious adverse events and unexpected device events will be recorded from study entry to completion. In addition, clinicians should monitor the safety of subjects by frequently asking them about their comfort during treatment delivery.

If skin erythema occurs, treatment will be discontinued. Patients will be instructed to contact the principal investigator of the study site or a member of his or her staff at any time between visits regarding adverse events or worsening of symptoms. If at any study visit, the subjects' clinical status significantly worsens from baseline (operationalized as the clinical global impression severity score, CGI-S, of 6 or greater) or if a subject develops active suicidal intent and/or plan, based on the C-SSRS scale and/or the clinical interview, the subject will be referred to the treating doctor to start an antidepressant medication or make appropriate changes in the treatment regimen. If the subject were considered to be in imminent danger as a result of suicidality, he/she would be discontinued from the study and referred to appropriate clinical treatment (see 4.9 Termination).

The two site principal investigators ([name], PI) will have bi-weekly conference calls (which will include all study staff); during these conference calls, they will discuss all adverse event reports to identify any safety concerns, based on such concerns, they may decide to temporarily discontinue study enrollment, modifications to the study protocol or terminate the study.

In addition, a Data and Safety Monitoring Board (DSMB), composed of at least 3 members not directly involved in the study, will review the SAEs annually. The research assistants responsible for data collection and storage will be aware of and comply with all regulatory requirements related to adverse events. In the event that a patient becomes ill or injured as a direct result of study participation, medical care will be provided. All adverse events (and device events) will be tracked to resolution and reported to the MGH or NKI IRB as serious in the event that:

Transcranial Near Infrared Laser Therapy in Subjects with Major Depressive Disorder: A Laser Dosing Study.

1. Not anticipated and possibly study-related (same report as SAE) or

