4.20 Summary of Risks and Benefits

4.20.1 Potential Adverse Events

Risks to the subject may include, but are not limited to, the following:

The EXPi device emits light with a wavelength longer than the human eye can see. Personnel will be trained in basic safety procedures related to the use of the device. Personnel administering the NIR-TLT will be careful not to operate the EXPi device unless it is in direct contact with the subject's skin. Both the subject receiving the NIR-TLT and the study doctor present in the NIR-TLT room will wear eye protection in the form of goggles or pads. The goggles provided with the EXPi device are in direct contact with the area surrounding the subject's eye. Since they are reusable, they should not be shared between subjects. The eye pads are disposable and should be discarded after use. The eye pads have an adhesive to adhere to the subject's eyelids, so there is a possibility of an allergic reaction.

EXPi device failure resulting in cessation of investigational therapy may cause:

1. No adverse events to our knowledge
2. Unforeseeable adverse events

Delivery of infrared energy to an inappropriate site, such as directly over the open eye, is not recommended and could pose a risk to the subject.

The application of the EXPi device may cause a slight thermal sensation of heat during use. The skin temperature is well below the thermal damage level.

Based on human clinical trial experience to date, each adverse event listed below has been reported with TLT:

1. Erythema at the application site
2. Pain at the application site
3. Discomfort at the application site
4. Heat at the application site
5. Reaction at the application site
6. Headache

Additional potential side effects of NIR-TLT, documented in previous trials, include:

- See bright colors, abnormal taste
- Feeling "out-of-body" experiences
- Insomnia, restless sleep, erratic sleep, early morning awakening.
- Vivid dreams
- Irritability
- Difficulty finding words
- Abdominal distention

Other potential risks are described below:

Transcranial Near Infrared Laser Therapy in Subjects with Major Depressive Disorder: A Laser Dosing Study.

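### Section 4.4.2 rests participant blinding on no dose feeling different from sham, but section 4.20.1 says the device may be felt as heat, so blinding is not assured on that ground

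*Protocol*

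**What the plan says.** Section 4.4.2 of the protocol treats participant blinding as secured and gives two reasons. The first is that the light cannot be seen: "Simulation blinding will be effective because the radiation is not visible". The second is that "no dose from the NIR-TLT will produce any perceptible difference from the simulation patient, e.g., skin heating".

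Section 4.20.1, on risks, says: "The application of the EXPi device may cause a slight thermal sensation of heat during use". It then gives a list introduced by "Based on human clinical trial experience to date, each adverse event listed below has been reported with TLT". The list includes "Heat at the application site" and "Erythema at the application site", as well as pain and discomfort at the site.

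Section 3.2 describes sham (Mode 4) as having no treatment site and "Average radiance: 0 mW / cm²". It equalises session length across modes, along with the display and everything that can be seen or heard. It describes nothing that would imitate warmth.

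Section 4.17.2 adds that "clinicians should monitor the safety of subjects by frequently asking them about their comfort during treatment delivery". Neither the visit procedures (4.9) nor the Table of Assessments includes a question on which arm the participant or rater believes was assigned.

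**The concern.** Section 4.4.2 is categorical, and its own example of what cannot be perceived is the sensation that section 4.20.1 warns about. Both statements are current text and they cannot both stand.

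The outcomes make this matter. HAM-D-17, the primary measure, is completed from an interview with the participant (4.10), and SAFTEE-SI, ASQ and SDQ are self-reported. A participant who feels warmth over repeated sessions may conclude that the laser is on and report accordingly. Laser warmth can arise only in the active arms, so such an expectancy effect would tend to favour laser over sham. The sample size in section 5.3 is built on an active-versus-control difference of 6.4 HAM-D-17 points, so this is the contrast the trial most needs to protect. If perceived assignment is never recorded, it cannot be recovered afterwards.

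**Working it through.** **1. The two statements side by side.** Section 4.4.2 says that no dose is perceptibly different from sham, with skin heating as the example. Section 4.20.1 says that a slight sensation of heat is possible with this device, and that heat at the site has been reported with the therapy. A slight sensation is still perceptible, so the softer wording of 4.20.1 does not reconcile them.

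**2. Whether the sham closes the gap.** Section 3.2 matches duration, display, sight and sound. A thermal match would be needed to support 4.4.2, and none is described.

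**3. The physical contrast between active and sham (inputs from 3.2).** Irradiance is 350 mW/cm², time 429 s, beam area 12 cm², and there are two sites.
- Fluence: 0.350 × 429 = 150.15 J/cm².
- Energy per site: 150.15 × 12 = 1,801.8 J, or 1.80 kJ. Both sites: 3.60 kJ. This reproduces the plan's 1.8 and 3.6 kJ.
- Power: 0.350 × 12 = 4.2 W per site, 8.4 W over both. Sham: 0 W.
- Sessions: 3 per week × 6 weeks = 18.

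The Summary and a later paragraph of 3.2 give 54.8 mW/cm² for this trial instead. That would yield 0.0548 × 429 = 23.5 J/cm², and 23.5 × 12 × 2 = 564 J, or about 0.56 kJ, which does not match the stated 3.6 kJ. The passages must be reconciled. On either figure the active arms emit and sham does not, so the contradiction in step 1 is unaffected.

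**4. Exposure before the ratings.** Section 4.9.2 has efficacy data collected before that day's laser. At visit 1 nobody has been exposed. By the ratings at visits 9 and 18, participants have had 8 and 17 sessions.

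**5. Who is affected.** Active arms: 3 × 28 = 84. Sham: 28. These are the numbers allocated to emitting and non-emitting modes. They are not counts of people who will or will not feel heat.

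**6. Whether a bias can be sized.** A simple form is bias = (share believing they are on active treatment in the active arms − the same share in sham) × shift in score due to that belief. The documents give neither the shares nor the shift, so the product cannot be evaluated.

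**7. Contrasts among active modes.** Modes 1 to 3 share the same average irradiance, exposure time and energy in 3.2. Nothing in the documents indicates that one would be felt more than another.

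**The case against.** The case for leaving the design alone has real content.

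- **Frequency is unknown.** Section 4.20.1 says only that heat may occur and is slight. It gives no rate and no excess over sham. A reader might infer that participants will be unblinded, or that 84 can feel heat and 28 cannot. The documents do not support that. They remove the stated guarantee but do not show failure.
- **Contrary evidence exists.** Section 4.3 cites sham-controlled stroke trials at 700 mW/cm², twice the 350 in 3.2, with no significant difference in adverse-effect rates. This stands, but those were single sessions in acute stroke, and an overall adverse-effect rate does not test whether warmth was noticed.
- **The skin-heating report in 4.3 concerns 10–15 W lasers,** which the protocol calls much higher power. It should not be used as evidence of heating here.
- **The earlier depression trial is not the basis of the claim.** A reader might argue that its blinding cannot carry over because its irradiance was lower. Section 4.4.2 does not rely on that trial, so the argument answers a claim the protocol does not make.
- **The rater has safeguards.** Only the participant and treating staff attend sessions (4.9.2), raters are to be unaware of assignment (4.11, 4.13), and scoring precedes that day's laser. It would be wrong to say that nothing shields the rater. What remains is narrower: clinicians ask about comfort during delivery, 4.20.1 mentions a study doctor in the room, and no text keeps notes from earlier sessions away from the rater.
- **Asking for a guess can itself prime participants.** This is a sound objection to asking at visits 1 or 9, before later primary ratings. It has little force after visit 18 scoring.

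None of this reconciles 4.4.2 with 4.20.1.

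**Conclusion.** The point holds in this form: participant blinding is not assured on the ground that section 4.4.2 gives, because section 4.20.1 contradicts that ground and the sham is not thermally matched. Confidence is high for the contradiction. That unblinding will happen, or how often, is not established.

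The exposure is confined to active-versus-sham comparisons on HAM-D-17 and the self-rated scales. It is not shown for pulsed-versus-continuous comparisons, so that part of Hypothesis 1 is not called into question here. A reader might want to express the bias as a fraction of the 6.4-point planning difference, but that would rest wholly on invented shares and shifts. No figure in the plan needs correcting for this point, and the sample size has no bearing on it. The change should be made, because perceived assignment can be recorded only while the trial is running.

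**What to change.** 1. Reconcile 4.4.2 with 4.20.1 and remove the categorical claim. State what is matched (duration, sight, sound) and that warmth is not known to be matched.
2. Give every arm the same instruction, namely that warmth may or may not be felt in any mode.
3. Add one item for the participant and one for the HAM-D-17 rater: guessed arm, certainty, and reason for the guess. Take it once, after all visit 18 ratings are scored, and report it by arm. Do not ask at visits 1 or 9. The reason matters because a guess at the end of treatment may reflect improvement rather than sensation, and the two need to be told apart.
4. State that the HAM-D-17 rater does not review in-session comfort or skin-inspection notes before scoring, where existing staffing allows. This leaves comfort monitoring and skin inspection as they are.
5. Reconcile two related conflicts: whether the device operator is blinded (3.2) or aware of assignment (Summary, 5.1), and which irradiance applies (54.8 mW/cm² in the Summary and a later paragraph of 3.2, 350 in the mode list of 3.2 and in 4.4).

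The cost is protocol wording and one short item for participant and rater at one existing visit. The drawback is possible slight priming before the week 8 follow-up rating, which comes after the visit 18 primary assessment.

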4.5 Study Population

4.5.1 Population Description

The subject population for this study will consist of 112 randomized subjects between the ages of 18 and 75 years, of any ethnicity and diagnosed with MDD. The subject will meet all inclusion criteria, will have none of the exclusion criteria, and will provide written informed consent to participate in this clinical trial. Any subject who signs an informed consent will be considered enrolled in the study, although they will not be able to participate if they are not eligible for the study. In the event that a subject's ability to understand and communicate is compromised (as assessed by the investigator), local regulations regarding informed consent signatures must be followed.

Subjects will be recruited, through selections, advertisements and publications. Study participants will also be recruited through advertisements on the Internet, study center websites, etc. According to the strategies proposed by each researcher.

Participants who contact the respective study site staff in response to any of the announcements will complete the telephone screening to determine tentative eligibility for the study.

4.5.2 Use in Female Subjects of Childbearing Potential

Women of childbearing age must consent (without any element of coercion) to use a double barrier method of birth control (e.g., condoms with spermicide) if they are sexually active. A pregnancy test will be performed at the screening visit. The sponsor will provide free access to any contraceptive method of the participant's choice.

4.5.3 Criteria for Enrollment - see inclusion and exclusion criteria section.

4.6 Subject Numbering

Subjects enrolled in the ELATED-4 study will be identified by subject numbers 01 through 150 (to account for selection failures and drop-out prior to randomization).

4.7 Sample Size

The study is expected to include 112 subjects with analyzable data (at least 3 sessions - 1 week, after randomization).

Near Infrared Transcranial Laser Therapy in Subjects with Major Depressive Disorder: A study of Dosing with Laser.

4.8 Subject Confidentiality

Any information and data provided to Pthera LLC or its designees in reference to any subject's participation in this research shall be considered confidential. The investigator shall ensure that the anonymity of all subjects is maintained in all documentation submitted to Pthera LLC by completely removing each subject's name and/or other identifying information. Identifying information will be replaced with the study number and subject's initials. The research site should not provide Pthera LLC with information such as subject phone numbers, home address, personal identification numbers such as passport numbers, etc. Site research personnel should be careful when communicating with Pthera LLC representatives by telephone or electronic correspondence not to provide information that could reveal a subject's identity.

Documents associated with the study that are not intended to be sent to Pthera LLC (e.g., signed informed consent forms) must be held in strict confidence by the investigator. Only study site personnel, authorized Pthera LLC personnel, and regulatory authority inspectors will have access to these confidential files.

4.9 Study Visits

The study includes screening tests, treatment and a series of follow-up visits.

4.9.1 Selection Visit - Week 0

Purpose

The purpose of the screening visit will be to determine the eligibility of patients to participate in the study.

Procedures

Study personnel will consent subjects to the study, perform a psychiatric evaluation, and screen for the presence of MDD using the MINI, QIDS-C, and CGI-S scales.

Laboratory tests (including urine collection for urine biochemical analysis and urine toxin analysis (also called Urine Drug Screen), urine pregnancy test, and a complete physical examination including vital signs and weight will be performed.

Approximately 15 cc \pm 5 cc (15 ml) of blood will be drawn for laboratory safety testing. To confirm that a patient is healthy enough to participate, a complete blood work-up with differentials, thyroid stimulating hormone test, blood biochemistry (glucose, calcium, sodium, potassium, carbon dioxide, chlorine, albumin, total protein, alkaline phosphatase, transaminases, total and fractionated bilirubins, urea, creatinine) and a high sensitivity C-reactive protein test will be performed. A PET scan will be performed on patients within the study subgroup to meet the exploratory objective.

Near Infrared Transcranial Laser Therapy in Subjects with Major Depressive Disorder: A study of Dosing with Laser.

Once all tests and procedures are available for review, study personnel will determine subject eligibility based on all inclusion and exclusion criteria.

Subjects who report having taken antidepressants at the screening examination may choose to continue medication during the study or taper and discontinue therapy prior to the baseline visit (under the supervision of a treating doctor). However, subjects who have discontinued more than two antidepressants in the current episode of depression will be excluded.

